Patients will be participating in the study for the duration of their surgery and for 24 hours after induction.

We anticipated it to take 1 year to enroll all study subjects.

We anticipate an extra 12 months after completion of the study for the investigators to complete the primary analyses.

6) Study Endpoints

The primary endpoints include:

- 1. Blood pressure changes during induction
- 2. Heart rate changes during induction

The secondary endpoints include:

- 1. Pain at injection
- 2. Myoclonic movements
- 3. PONV in PACU
- 4. Postoperative pain score
- 5. Incidence of adverse reactions during induction
- 6. Severity of adverse reactions during induction

7. Dose and frequency of vasoactive agents and other concomitant medications used to treat adverse reactions of propofol / etomidate

8. Sedation depth using bispectral index (BIS)

- 9. Eyelash reflex disappear time
- 10. Intubation time
- 11. Dose and frequency of analgesic and other sedatives used

7) **Procedures Involved**

This is a non-blinded, randomized, parallel-group study in patients scheduled for elective surgery under general anesthesia and orotracheal intubation to compare etomidate plus propofol vs. propofol or etomidate alone on induction of anesthesia.

There will be three cohorts of 25 patients per cohort with one cohort administered propofol, one cohort administered etomidate, and one cohort administered propofol

etomidate. The sample size was calculated with the blood pressure change \pm 20 mmHg, SD \pm 25 mmHg, power of 0.80 and p value of 0.05 and resulted 25 in each group.

The research team will create 75 envelopes. Each will be numbered, 25 will be in propofol group, 25 will be in etomidate group and 25 will be in propofol/etomidate group. On the day of surgery, one envelope will be randomly picked for each participant.

Patients in the three cohorts will be administered a 30 second bolus by manual hand push.

Intensive PD and safety assessments will be performed prior to dosing on Day 1 until 24 hours post-dose (Day 2). There are no plans for long-term follow-up past the 24 hours.

Three cohorts are as follow:

- 1. Propofol group: 2 mg/kg propofol
- 2. Etomidate group: 0.3 mg/kg etomidate
- 3. Propofol plus etomidate group: 1mg/kg propofol plus 0.15mg/kg etomidate.

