Systolic blood pressure, diastolic blood pressure, mean arterial pressure, heart rate will be monitored and recorded before induction, at induction and intubation followed by 1, 3, 5 and 10 minutes after intubation.

Pain on injection will be measured using 4 graded scale; 0 --- no pain, 1 --- verbal complaint of pain, 2 --- withdrawal of arm, 3 --- both verbal complaint and withdrawal of arm.

The incidence and degree of myoclonic movements also recorded as follows: 0 = no myoclonic movements, 1 = minor myoclonic movements, 2 = moderate myoclonic movements, 3 = major myoclonic movements.

The medications used in the 3 groups are clinically used already with FDA approval for their use. This is an observational study and we will compare the effects of the three groups with their medication uses on the parameters we listed above: systolic blood pressure, diastolic blood pressure, mean arterial pressure, heart rate, pain on injection, myoclonic movements, PONV and BIS numbers.

Non-English speaking participants are still eligible for the study. We will use translation services in line with HRP 090 and HRP 091 and the consent short form to enroll interested non-English speaking participants. If we find that we have enrolled 2 patients of a particular language using the short form as the study progressed, we will obtain full translation of the consent form into that language through the use of UCD Translation Services.

8) Data and/or Specimen Management and Confidentiality

All data will be summarized using descriptive statistics. Summaries of continuous variables will present mean, median, standard deviation, minimum, and maximum; summaries of categorical variables will present frequencies and percentages. All data will be presented in subject data listings.

Subject enrollment and disposition, including reasons for early withdrawal from the study, will summarized by group.

Demographic variables will be summarized by group for all enrolled subjects. Data will be stored up to 3 years after finishing the study.

This is a pilot study with a proposal to enroll 25 patients into each group for a total of 75 patients randomized.

We expect to complete data analysis on 20 patients in each group for a total of 60 patients due to patient withdrawal either voluntarily or due to formal withdrawal criteria, ie difficulty with securing patient airway.

9) Provisions to Monitor the Data to Ensure the Safety of Subjects

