As this is a minimal risk study, there are no plans to monitor the data.

10) Withdrawal of Subjects

The PI and research team can withdraw subjects from the study without their consent if difficulty securing their airway is encountered.

11) Risks to Subjects

The potential risks are breack to confidentiality and risks associated with the study drugs, Propofol and Etomidate.

In order to safeguard our patient's confidential data and to lessen the likelihood of a breach of confidentiality, the following parameters will be put in place:

- 1. The data will be stored in the PI's password-protected computer in his locked office.
- 2. We don't anticipate needing to transport any data, but if need be, the data will be transported via a hospital issued, password protected IRONKEY.
- 3. Patients' names and medical record numbers will be used initially. A numerical number (0001 to 0050) will be assigned to each patient.

- 4. If the data need to be transmitted, the UCD secured email system will be used and the receiving end needs to be same secured email system.
- 5. Only the research team members can access the data.

Risks associated with Propofol and Etomidate :

Risk of Etomidate:

Transient venous pain on injection

Transient Skeletal muscle movements

Respiratory System: Hyperventilation, hypoventilation, apnea of short duration, laryngospasm, hiccup and snoring suggestive of upper airway obstruction.

Circulatory System: Hypertension, Hypotension, tachycardia, bradycardia, arrhythmias

Risks of Propofol:

Cardiovascular: Bradycardia, arrhythmia, tachycardia, hypotension, decreased cardiac output

Central nervous system: movement

Metabolic/Nutritional: Hyperlipemia

Respiratory: Apnea, respiratory acidosis during weaning

Skin and appendages: Rash, pruritus

12) Potential Benefits to Subjects

Both propofol and etomidate are used in everyday clinical practice. There are still controversial over which out of the two is better. By using the combination of etomidate and propofol at a reduced dosage in cohort 3, we hope that patients can benefit from those drugs through the minimization of side effects.

We are unable to tell if there will be a direct benefit to the study participant.

13) Multi-Site Research

N/A

14) Community-Based Participatory Research

N/A

15) Sharing of Results with Subjects

There are no plans to share study results with participants.

16) Prior Approvals

N/A

17) Provisions to Protect the Privacy Interests of Subjects

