Eligible patients will be screened through electronic medical record review up to 48 hours before their scheduled elective surgery. Patients will be approached on the day of the surgery in the UC Davis preoperative holding area of the main hospital to gauge for study interest. Research team will obtain consent from interested participants and honor any withdrawal requests based off of randomization group or time-constraints.

This observational study does not allow for any interventions nor study procedures outside of the patient's normal care, so we will limit unnecessary interactions with the patients to minimize the sense of intrusiveness a subject might experience in response to standard questions, examinations, and procedures.

The research team will complete the HIPPA and required CITI training. Only at the time of data collection can the research team access the necessary patient's information.

18) Compensation for Research-Related Injury

There is no compensation for participating in this minimal risk study.

19) Economic Burden to Subjects

Both medications are already routinely ordered and administered, and will be billed accordingly to the patient's insurance.

20) Drugs or Devices

This is an observational study using FDA-approved medications that are used in everyday practice for anesthesia induction purpose.

Medication is routinely stored in PYXIS and will be taken by the anesthesiology.

21) ClinicalTrials.gov Registration

Section 1: NIH Funded Studies

If yes to BOTH, the study must be registered on Clinicaltrials.gov.

Yes	
	This study is funded by the NIH . (If this study is not funded by NIH, go to
	Section 2.)
	One or more human subjects will be prospectively assigned to one or more
	interventions (which may include placebo or other control) to evaluate the effects
	of those interventions on health-related biomedical or behavioral outcomes.

Section 2: Studies subject to FDA jurisdiction

If yes to ANY the study must be registered on Clinicaltrials.gov.

 This is a prospective clinical study of health outcomes in human subjective compares an intervention with an FDA-regulated device against a correst is not a small clinical trial to determine the feasibility of a device, or a small clinical trial to determine the feasibility of a device. 	jects that ontrol. This a clinical
trial to test prototype devices where the primary outcome measure relation feasibility and not to health outcomes.	elates to

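### The protocol accepts withdrawal because of the allocated arm, leaves the time of the envelope draw open, and defines no analysis set, so arm-dependent loss after randomization is possible and unhandled

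*Protocol*

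**What the plan says.** Five parts of the protocol and the SAP bear on this point.

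- **Consent and withdrawal (protocol section 17).** "Patients will be approached on the day of the surgery in the UC Davis preoperative holding area of the main hospital". Interested patients then give consent, and the team will "honor any withdrawal requests based off of randomization group or time-constraints".
- **Allocation (section 7).** "This is a non-blinded, randomized, parallel-group study". There are 75 numbered envelopes, 25 per arm, and "On the day of surgery, one envelope will be randomly picked for each participant". The hour, the place and the order relative to consent and induction are not given.
- **Outcome timing (sections 5 and 7).** Blood pressure and heart rate are "recorded before induction, at induction and intubation followed by 1, 3, 5 and 10 minutes after intubation". Only the first of these readings precedes the drug. Participation lasts until 24 hours after induction.
- **Other withdrawal text (sections 8 and 10).** Under section 10 the team may "withdraw subjects from the study without their consent if difficulty securing their airway is encountered". Section 8 plans to "enroll 25 patients into each group for a total of 75 patients randomized" and expects 20 per arm (60 in all) to be analyzed, with the loss "due to patient withdrawal either voluntarily or due to formal withdrawal criteria". Withdrawal reasons are to be summarized by group.
- **SAP.** It allows for 20% dropout, taking 20 per group up to 25, and compares hemodynamics with a repeated-measures general linear model. Neither document defines the population for the endpoint comparisons, a missing-data method or a replacement rule.

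**The concern.** A request to withdraw because of the randomization group can be made only once the arm has been drawn and disclosed. The protocol thus foresees that some patients will know their arm and leave on account of it. In a non-blinded trial with no fixed draw time, nothing stops this from happening before the drug is given.

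The protocol also supplies reasons for disliking particular arms. Section 3 links propofol to injection pain and hypotension, and etomidate to myoclonus and PONV. It also cites a retrospective study associating etomidate with higher 30-day mortality. Patients who leave an arm for such reasons may differ in prognosis from those who stay. The remaining groups would then no longer be the groups that randomization made comparable.

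A patient who leaves before dosing, and is not followed further, has at most a baseline reading and adds nothing to the comparison of responses over time. Summarizing reasons by group would show an imbalance but would not correct it.

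Withdrawal for lack of time is a smaller matter. It need not differ by arm, but if it follows the draw it uses one of only 75 envelopes, and no replacement is described.

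**Working it through.** **1. The plan's own figures.** Protocol section 7 uses a difference of 20 mmHg, SD 25 mmHg, power 0.80 and alpha 0.05 (two-sided assumed):

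n = 2 × (1.960 + 0.842)² × 25² / 20² ≈ 24.5, so 25 per group, as stated.

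The SAP's dropout step gives 20 / (1 − 0.20) = 25, as stated. The planned loss is therefore 5 of 25 (20%) per arm, or 15 of 75. How it divides between airway difficulty, patient request and lack of time is not given.

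**2. Sequence of events.**

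| Step | What the documents fix | What they leave open |
|---|---|---|
| Approach and consent | Day of surgery, preoperative holding | Order relative to the draw |
| Envelope draw | Day of surgery | Hour and place |
| Arm known to patient | Implied by the section 17 wording | When |
| Drug given, first outcome reading | Induction | – |
| Withdrawal request | Accepted, including because of arm | Before or after dosing |

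A draw in holding and a draw in the operating room both fit the text. Loss by arm before dosing is permitted, but it is not shown to be what will happen.

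**3. Illustrative size.** Let k of 25 patients leave one arm, and let their mean differ by d from that of the patients who stay. The mean of the stayers then differs from the mean of the full arm by

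shift = (k / 25) × d.

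Both k and d are assumptions. The SAP gives MAP at induction as 80.1 mmHg in group P and 90.3 mmHg in group PE, a difference of 10.2 mmHg.

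| k | d = 5 mmHg | d = 10 mmHg |
|---|---|---|
| 2 | 0.4 mmHg | 0.8 mmHg |
| 3 | 0.6 mmHg | 1.2 mmHg |
| 5 | 1.0 mmHg | 2.0 mmHg |

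The range is 0.4 / 10.2 = 4% to 2.0 / 10.2 = 20% of the PE−P difference. This is the shift in one arm. If two arms lose patients selectively, the shifts may add or cancel in the contrast.

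**4. Against sampling error.** With 20 per arm and the SAP's SDs of 10.3 and 10.4, the standard error of the PE−P difference is √((10.3² + 10.4²) / 20) = √10.71 = 3.27 mmHg. The illustrated shifts are 0.4 / 3.27 = 0.12 to 2.0 / 3.27 = 0.61 standard errors.

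**The case against.** The strongest reply is that section 17 states an ordinary right to withdraw, that the loss is already budgeted at 20%, and that withdrawal reasons are reported by group, so an imbalance would be visible. The trial also calls itself a pilot. All of that is correct. But the allowance protects numbers, not comparability, and the reporting is only descriptive.

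A reader might also draw several stronger conclusions that the documents do not support.

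- **That the envelope is drawn early and patients leave before any outcome exists.** Only the day is stated. A request could also come after dosing, at any time up to 24 hours after induction.
- **That sections 10 and 17 contradict each other.** Section 10 concerns removal by the team without consent. Section 17 is most naturally read as requests from patients. Section 8 names both routes, so they complement each other.
- **That clinicians may take a patient out because of the arm.** Nothing says so. Airway difficulty is the only ground stated for removal by the team.
- **That no analysis could recover these patients.** Someone who declines the allocated drug still has surgery under anesthesia. If that patient permits data use, outcomes can be recorded and analyzed by randomized group. Only a patient who also refuses data use is lost.
- **That lack of time is an arm-related reason.** By its terms it is not.
- **That a bias of known size or direction is established.** The top illustrated case needs the whole planned loss in an arm to be driven by allocation, with leavers about 1 SD different (10 / 10.3 = 0.97). The documents give no basis for choosing k, d or the sign of d.

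**Conclusion.** The point holds in a limited form. The protocol accepts withdrawal prompted by the allocated arm in a non-blinded trial, does not fix when the arm becomes known, expects about a fifth of each arm to go unanalyzed, and states no analysis set. Selective loss by arm is therefore possible and, beyond a summary of reasons, unaddressed.

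Its actual size cannot be determined from the documents. The 0.4 to 2.0 mmHg range rests wholly on the assumed number of leavers and their assumed difference, and even the top of it is well under one standard error of the PE−P difference. The conclusion that the loss can depend on the arm needs none of those assumptions. It follows from the section 17 wording, the open-label design and the unspecified draw time.

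This is a cheap improvement worth making, not a flaw that invalidates the trial.

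**What to change.** - **Section 7.** State that the envelope is drawn in the operating room immediately before the induction drug is prepared. Before the draw, the patient's willingness to accept any of the three arms is reconfirmed, and the team confirms that there is time for the study procedures. A patient lost before this point is not randomized and uses no envelope, so all 75 allocations remain available.
- **Section 17.** Keep the right to withdraw at any time for any reason. Add that a patient who declines the allocated drug is asked whether data may still be used and, if so, has the outcomes recorded.
- **SAP.** Define the analysis set so that these patients are analyzed in the group to which they were randomized.

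Merely deleting the section 17 phrase would change nothing, since an unrestricted right to withdraw includes leaving because of the arm. No restriction on the clinical team is proposed, because that would touch clinical discretion.

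The cost is a short amendment to two protocol sections and one addition to the SAP, with no change in the number randomized. The team has slightly shorter notice of the arm, and a few more patients may need to be approached for consent. A late draw reduces arm-driven withdrawal but does not abolish it, since an awake patient in an open-label trial can still learn the arm and leave.

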Title: Comparison of Etomidate Plus Propofol, Etomidate Alone on Induction of Anesthesia

NCT03820388

Document Date: September 26, 2017

Statistical Analysis

Sample size calculations were based on our pilot study, and we found MAP to be 80.1 (± 10.3) mmHg, 90.3 (± 10.4) mmHg, 91.0 (± 11.6) mmHg in group P, PE and E at induction. Using PASS 15.0 software, a sample size of 20 patients per group would be needed to detect statistically significant differences with the power of 0.9 and the alpha level of 0.05. Considering a possible 20% dropout rate, 25 patients per group were recruited for the study.

Parametric values were expressed as mean (SD), or percentages of the total number of patients (%). Categorical data were analyzed using χ^2 or Fisher's exact test as appropriate. The hemodynamic parameters among the three groups were compared using the general linear model (GLM). We also considered time of evaluation as a within-subject factor, and the intervention state as a between-subject factor. The time groups (interaction terms) were considered group differences among the three groups in their responses over time. We used Mauchly's sphericity test for compound symmetry assumption. Differences in hemodynamic variables between the three groups at different time points were compared by post hoc Bonferroni test. $P < 0.05$ was considered statistically significant. All statistical analyses were performed with SPSS 22.0 (SPSS; Chicago, IL, USA).

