Title: Comparison of Etomidate Plus Propofol, Etomidate Alone on Induction of Anesthesia

NCT03820388

Document Date: March 15, 2017

1) **Protocol Title**

Comparison of Etomidate Plus Propofol vs. Propofol, Etomidate Alone on Induction of Anesthesia, a Pilot Observational Study

Protocol Version Date: 5/2/2017

2) Objectives

The purpose of this study is compare of etomidate plus propofol vs. propofol or etomidate alone during induction of anesthesia.

The specific aims or objectives are testing patient reactions during induction, and in the post anesthesia care unit (PACU).

The hypotheses to be tested: induction with etomidate combined with propofol when compared to induction with propofol or etomidate alone:

1. will provide less pain during injection,

2. less hypotension (compare to propofol), less hypertension (compare to etomidate) and better hemodynamics than propofol or etomidate during induction,

3. Similar postoperative nausea and vomiting (PONV) when compared with propofol and less PONV when compared with etomidate,

4. Similar pain score among all three groups

3) Background

Induction of anesthesia is a critical part of anesthesia practice. Sudden hypotension, hypertension, arrhythmias, and cardiovascular collapse are threatening complications following injection of induction agent in hemodynamically unstable patients. It is desirable to use a safe agent with fewer adverse effects for this purpose.

Both etomidate and propofol are the most commonly used induction agents for general anesthesia (GA) and both propofol and etomidate have their advantages and disadvantages. Propofol has been associated with injection pain, significant hemodynamic change (hypotension) during induction and less PONV. Etomidate has been associated with more stable hemodynamic and less pain during induction, but more myoclonic movements at induction and PONV. However, those findings are still controversial and the published results are still inconsistent.

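### The protocol's power of 0.80 needs all 25 patients per group but only 20 are expected to be analysed (power about 0.69); the SAP's 0.9 should not be read as power for the combination versus propofol

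*SAP*

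**What the plan says.** **Protocol.** Section 7 (Procedures Involved) bases the sample size on a blood pressure change of 20 mmHg with SD 25 mmHg, "power of 0.80 and p value of 0.05 and resulted 25 in each group". Section 8 (Data and/or Specimen Management and Confidentiality) gives a smaller number for analysis, because of withdrawals: "We expect to complete data analysis on 20 patients in each group for a total of 60 patients". Hypothesis 2 in section 2 (Objectives) sets the combination against each single agent: "less hypotension (compare to propofol), less hypertension (compare to etomidate) and better hemodynamics than propofol or etomidate during induction".

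**SAP (Statistical Analysis).** This is a separate calculation. It takes pilot MAP at induction of 80.1 (SD 10.3), 90.3 (SD 10.4) and 91.0 (SD 11.6) mmHg for P, PE and E, and concludes that "a sample size of 20 patients per group would be needed to detect statistically significant differences with the power of 0.9" at alpha 0.05. It then allows for losses: "Considering a possible 20% dropout rate, 25 patients per group were recruited for the study". No test, contrast or sidedness is named for the 0.9. The planned analysis is a general linear model across the three groups with time as a within-subject factor, followed by pairwise testing: "Differences in hemodynamic variables between the three groups at different time points were compared by post hoc Bonferroni test". The SAP does not say how many comparisons the Bonferroni correction covers.

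**The concern.** The protocol reaches 25 per group as the number needed for analysis, then plans for a fifth of those patients not to be analysed. Its stated power therefore belongs to a number of patients that it does not expect to have. The SAP also arrives at 25 per group, but from different inputs, with a different power and with dropout built in. Neither document says which calculation governs.

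The second issue is interpretation. The SAP's 0.9 is attached to unspecified differences among three groups, while hypothesis 2 and the post hoc test turn on pairs. Someone planning from the SAP, or interpreting a non-significant PE versus P result, could take 0.9 as the power for that pair and so overstate the chance of a positive result. Likewise, a non-significant PE versus E result could be taken as evidence of similarity that this sample size cannot give.

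**Working it through.** **1. The protocol's figure.** Inputs from Protocol section 7: difference 20 mmHg, SD 25 mmHg, alpha 0.05, power 0.80. A two-group, two-sided, unadjusted comparison is assumed; the protocol does not state this, but it reproduces the stated number.

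- Normal approximation: n = 2 × (1.96 + 0.8416)² × (25/20)² = 24.5, so 25 per group. The stated figure reproduces, with nothing added for dropout.
- At 25 per group the standard error is 25 × √(2/25) = 7.071 and the noncentrality is 20/7.071 = 2.828. Power is 0.81 by normal approximation and 0.79 by the t test (48 df).
- At the 20 per group in Protocol section 8 the standard error is 25 × √(2/20) = 7.906 and the noncentrality is 20/7.906 = 2.530. Normal approximation: Φ(2.530 − 1.960) = Φ(0.570) = 0.72. t test (38 df, critical value 2.024): 0.69.

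The gap between 0.80 and 0.79 is only t test versus normal approximation. The fall to 0.69 comes from losing 5 of 25 patients per group.

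**2. The SAP's figure.** Inputs from the SAP: the three pilot means and SDs, alpha 0.05, 20 per group.

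- Pooled SD = √((10.3² + 10.4² + 11.6²)/3) = √116.27 = 10.78.
- The mean of the three means is 87.13. The deviations are −7.03, 3.17 and 3.87, and their squares sum to 74.45.
- Overall F test noncentrality: 20 × 74.45/116.27 = 12.81. With 2 and 57 df (critical value 3.159), power is **0.887**. At 21 per group it is 0.903.
- Dropout: 20/0.8 = 25, as stated.
- With PE and E both set to their average, 90.65, the overall power is 0.886. The overall result is therefore driven by the lower P mean.

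The 0.9 fits an overall three-group test approximately. Two other tests also come close at 20 per group: unadjusted two-sided P versus E (0.87-0.88) and unadjusted one-sided PE versus P (0.91-0.92). The documents do not settle which was used.

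**3. PE versus P at 20 per group.** The difference is 90.3 − 80.1 = 10.2 mmHg at one time point, tested two-sided. Two SDs are used: the pair SD, √((10.3² + 10.4²)/2) = 10.35 with 38 df, and the three-group SD, 10.78 with 57 df.

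- Noncentrality: 10.2/(10.35 × √0.1) = 3.116, or 10.2/(10.78 × √0.1) = 2.99.

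| Alpha | Pair SD, n = 20 | Pooled SD, n = 20 | Pair SD, n = 25 | Pooled SD, n = 25 |
|---|---|---|---|---|
| 0.05, unadjusted | 0.859 | 0.837 | 0.927 | 0.910 |
| 0.05/3, three pairs (assumed) | 0.727 | 0.699 | 0.838 | 0.812 |

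Power of 0.9 for this pair needs 23-25 evaluable per group unadjusted, or 30-32 at 0.05/3.

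A simulation of 40,000 trials from the SAP's means and unequal SDs at 20 per group agrees. The overall test is significant in 89% of trials and PE versus P at 0.05/3 in 71%. In 19% the overall test is significant without PE versus P.

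**4. PE versus E at 20 per group.** The pilot difference is 91.0 − 90.3 = 0.7 mmHg, for which power is about 0.05. For 80% power the difference would have to be 9.7-10.0 mmHg unadjusted, or 11.3-11.7 mmHg at 0.05/3. The confidence interval half-width is 6.8-7.1 mmHg unadjusted and 8.4-8.7 mmHg at 0.05/3.

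**The case against.** The strongest reply is that the SAP's number is sound and that the SAP never assigns it to PE versus P. That stands: 0.887 is close to 0.9, an overall test matches the three-group model in the SAP, and what is missing there is the name of the test. The harm arises only if a reader carries the figure over.

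Other points in the plan's favour:

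- **The later SAP has its own calculation.** True, and it allows for dropout. But it does not say that it replaces the protocol's, so the 0.80 still stands beside an expected 20 analysed.
- **All 25 per group may be evaluable.** Then the protocol's power is 0.79 and unadjusted PE versus P reaches 0.91-0.93, although at 0.05/3 it is still 0.81-0.84. Both documents, however, plan for 20.
- **A one-sided PE versus P test reaches 0.91-0.92.** Correct if unadjusted, but nothing in the SAP indicates one-sided testing, and it plans Bonferroni.
- **The Bonferroni family is assumed.** It is. Three pairs is the natural reading of post hoc comparisons between three groups, but the SAP does not say so. A reader might go further and spread the correction over all seven recorded times, which gives a much lower power; the documents define no such family.
- **The unadjusted shortfall is modest.** It is 0.84-0.86 against 0.9, and it depends on pilot values whose precision cannot be judged because the pilot's size is not given.

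**Conclusion.** The protocol's power is wrong as written. At the 20 per group it expects to analyse, its own inputs give about 0.69 (0.72 by normal approximation) rather than 0.80. This assumes a two-sided, unadjusted comparison of two groups.

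The SAP point is secondary and is one of labelling. Its 0.9 approximately fits an overall test of MAP at induction. It does not describe PE versus P, where two-sided power at 20 per group is 0.84-0.86 unadjusted and about 0.70-0.73 if Bonferroni covers three pairs. These figures rest on the pilot means and SDs, a single time point and, for the lower range, an assumed family.

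A reader might infer that the SAP miscalculated its sample size, or that the main analysis is underpowered. The documents support neither. The first reproduces to within about one patient per group. The second cannot be assessed, because the power of the repeated-measures group-by-time test depends on within-patient correlations and later time-point means that are not given.

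**What to change.** 1. **Protocol, section 7.** Restate the power as about 0.69 at 20 evaluable per group for 20 mmHg and SD 25 mmHg (two-sided, unadjusted), or state that the SAP calculation supersedes it.
2. **SAP, sample size.** Keep the existing sentence as the record of the PASS calculation. Ask the trial team which test was entered and, if they confirm it, label the 0.9 as the overall three-group test of MAP at induction.
3. **SAP, added sentence**, dated and marked as to whether data had been seen. For example: With 20 evaluable patients per group, two-sided power for PE versus P in MAP at induction is 0.84-0.86 unadjusted and about 0.70-0.73 with Bonferroni over three pairs; the sample size was not set to detect the pilot PE versus E difference of 0.7 mmHg. State the Bonferroni family actually used.
4. **Reporting.** Give PE versus E as an estimate with a confidence interval at the level that matches the test.

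The cost is wording and a less favourable stated power. No patients, tests, endpoints or hypotheses change.

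### Two hypotheses claim similarity (PONV against propofol; pain score across all three groups), but the plan has only difference tests and no criterion for similar

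*SAP*

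**What the plan says.** Protocol section 2 (Objectives) introduces its list with "The hypotheses to be tested: induction with etomidate combined with propofol when compared to induction with propofol or etomidate alone". Hypothesis 3 reads "Similar postoperative nausea and vomiting (PONV) when compared with propofol and less PONV when compared with etomidate" and hypothesis 4 reads "Similar pain score among all three groups". Both correspond to secondary endpoints in protocol section 6: PONV in the PACU, and "Postoperative pain score".

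For analysis, the SAP states "Categorical data were analyzed using χ^2 or Fisher's exact test as appropriate", with significance at P < 0.05. It applies the general linear model and the post hoc Bonferroni comparisons to hemodynamic variables only. Other continuous values are given as mean (SD). Protocol section 8 adds "All data will be summarized using descriptive statistics" and, on numbers, "We expect to complete data analysis on 20 patients in each group", out of 25 randomized per group.

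Neither document contains a margin, an interval for a group difference, an expected PONV rate, or a scale, time point or SD for the postoperative pain score.

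**The concern.** A chi-square or Fisher test can reject equality; failing to reject does not establish it. Hypothesis 4 and the first half of hypothesis 3 are claims of no important difference, so the planned tests do not address them. The second half of hypothesis 3, less PONV than etomidate, is an ordinary difference claim and is not at issue.

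Two further gaps make this worse. The SAP does not say whether the categorical test is run pairwise or once across three groups, and a single three-group test does not show whether the combination resembles propofol or etomidate. For the pain score no between-group test is named at all, unless the score is categorized and falls under chi-square or Fisher.

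What is at stake is whether the trial can say anything about similarity. As planned, either claim would rest on a non-significant P value or on summaries read side by side.

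**Working it through.** **1. The plan's own sample-size figures.** These are for blood pressure.
- SAP: MAP means 80.1, 90.3 and 91.0; SDs 10.3, 10.4 and 11.6. Pooled variance = (106.09 + 108.16 + 134.56)/3 = 116.27, so SD = 10.78. The squared deviations of the means sum to 74.45. Noncentrality at n = 20 is 20 × 74.45/116.27 = 12.8. One-way ANOVA power is 0.887 at 20 per group, and 21 are needed for 0.90. Dropout: 20/(1 − 0.20) = 25. The stated 20 and 25 are reproduced to within one patient.
- Protocol section 7: 2 × (1.960 + 0.842)² × 25²/20² = 24.5, so 25 per group, as stated.

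Both calculations size the trial to detect blood-pressure differences. Neither bears on similarity of PONV or pain.

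**2. PONV, pairwise test of combination against propofol.** The rates are assumptions. The probability of P ≥ 0.05 was found by enumerating all pairs of binomial counts. The SAP does not define when each test is appropriate, so three rules are shown: uncorrected chi-square / Fisher / chi-square switching to Fisher when an expected count is below 5.

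| True rates | n = 20 | n = 25 |
|---|---|---|
| 10 vs 30% | 0.643 / 0.758 / 0.710 | 0.550 / 0.695 / 0.591 |
| 20 vs 40% | 0.709 / 0.808 / 0.716 | 0.648 / 0.769 / 0.649 |
| 30 vs 50% | 0.755 / 0.837 / 0.755 | 0.666 / 0.768 / 0.666 |
| 20 vs 20% | 0.950 / 0.977 / 0.967 | 0.945 / 0.978 / 0.956 |

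Non-significance is the likely result whether the rates are equal or 20 points apart.

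**3. PONV, one three-group chi-square (2 df).** Probability of P ≥ 0.05, rates in the order propofol/combination/etomidate:

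| Scenario | Rates (%) | n = 20 | n = 25 |
|---|---|---|---|
| Combination equals propofol | 10/10/30 | 0.615 | 0.547 |
| | 20/20/40 | 0.700 | 0.648 |
| | 30/30/50 | 0.746 | 0.697 |
| Combination equals etomidate | 10/30/30 | 0.677 | 0.596 |
| | 20/40/40 | 0.735 | 0.677 |
| | 30/50/50 | 0.761 | 0.703 |

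The first scenario fits hypothesis 3 and the second contradicts it, yet the test behaves almost the same in both.

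**4. What an interval would show.** The approximate 95% half-width for a PONV difference with common rate p is 1.96 × √(2p(1 − p)/n). At p = 0.20 this is 1.96 × √(0.32/20) = 0.248 for n = 20, and 0.222 for n = 25.

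For illustration, take a margin of ±20 points (assumed) and Newcombe 95% intervals:
- True difference 20 points: the interval lies inside the margin in at most 0.8% of trials. Reading P > 0.05 as similar is wrong in 55-84% (step 2).
- Equal true rates of 10/20/30%: the interval lies inside the margin in 8.8/0.3/0.0% of trials at n = 20 and 19.6/2.4/0.1% at n = 25.
- Upper limit only below +20 points (one-sided 0.025), equal rates of 10/20/30%: met in 47.7/36.0/31.4% at n = 20 and 58.6/44.4/37.0% at n = 25. If the combination is truly 20 points worse, it is met in 2.7-3.6%.

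**5. Pain score, in SD units because no SD is given.** The 95% half-width for a pairwise difference is t(0.975, 2n − 2) × √(2/n): 2.024 × √(2/20) = 0.640 SD at n = 20, and 2.011 × √(2/25) = 0.569 SD at n = 25. A true difference of 0.5 SD is non-significant in 66% and 59% of trials (noncentral t).

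**The case against.** The strongest reply is that this is a pilot, that both endpoints are secondary, and that the SAP nowhere says a non-significant test will be read as similarity. In that setting 'similar' may only state an expectation. The point about weight stands: this is an improvement to make, not a flaw in the main analysis. But the protocol lists both claims as hypotheses to be tested and offers no other way to judge them.

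The headline range is also fairly challenged. Its ends come from applying one test regardless of cell counts. Under the switching rule it narrows to 71-76% at n = 20 and 59-67% at n = 25. That is one reading of a rule the SAP leaves undefined, and the conclusion is the same. Likewise, the three-group figures use chi-square even where cells are sparse (94% of tables at 10/10/30, n = 20), and hypothesis 3 itself points to pairwise comparisons. The three-group results show what follows if the SAP's silence is filled that way.

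Finally, the interval rule rarely errs partly because it rarely passes anything. A 90% interval with the same ±20-point margin passes more often under equal rates: 27-45% at 10% PONV, 7-15% at 20% and 1-4% at 30%. The small sample, and not only the SAP's wording, limits what can be claimed. That is an argument for treating the claims as estimates.

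**Conclusion.** The concern holds. The plan followed as written cannot support PONV similar to propofol or similar pain scores across the groups, because its tests address difference only and no criterion for similarity is given.

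Under assumed PONV rates of 10-50%, a 20-point difference goes undetected in more than half of trials under every test rule considered. A half-SD pain difference goes undetected in about 6 of 10 or more. These figures rest on assumed rates, a pairwise comparison, two-sided 0.05 and 20 to 25 analyzed per group. The lack of a criterion does not depend on them.

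The missing name of a pain-score test is, on its own, only missing detail. The claims affected are secondary.

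**What to change.** Add to the SAP:

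1. The PONV difference, combination minus propofol, and the pairwise pain-score differences will be reported with 95% confidence intervals.
2. P > 0.05 will not be read as similarity.
3. Both similarity claims are treated as estimates unless the interval lies within a justified margin fixed before analysis. The SAP is written in the past tense; if analysis has already begun, a margin can no longer be set in advance and the claims stay as estimates.
4. The between-group analysis of the postoperative pain score is named, with its scale and time point, and the PONV comparison with propofol is stated to be pairwise.

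The cost is a few sentences and no extra patients or data. The downside is that a formal two-sided similarity conclusion will seldom be reached at this size. A one-sided criterion (combination not worse by more than the margin) has a better chance, about 31-59% with equal rates of 10-30% and an assumed 20-point margin, but it makes a weaker claim than similarity.
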